12.2.2. Control of Systematic Error/Bias

Selection of subjects will be made from the Investigator's usual patient load. All subjects meeting the inclusion/exclusion criteria and having signed the Informed Consent Form will be eligible for participation in the registry. The reasons for exclusion, for patients who sign an informed consent form but do not proceed to a neurostimulation trial, will be indicated in the patient screening log. Consequently, consecutively eligible patients will be allocated into the study, minimizing selection bias. Boston Scientific will report to the applicable agency any evidence of fraud, including deliberate tampering with the selection of subjects.

A chest-worn biosensor patch, a wrist-worn biosensor and eDiary Application will be provided to all patients enrolled in the study. Patients are reminded to complete questionnaires on a schedule and monitored during the study duration.

12.3. *Data Analyses*

All consented subjects will be included in analyses. Subjects who wear a chest-worn biosensor patch, and/or a wrist-worn biosensor will be included in safety analyses.

12.3.6. Changes to Planned Analyses

Any changes to the planned statistical analyses will be documented. Rationale for changes to planned analyses as noted in this protocol will be included in the final study report and other reports, as applicable.

13. Data Management

13.1. *Data Collection, Processing, and Review*

Subject study data will be recorded in a limited access secure electronic data capture (EDC) system. The chest-worn biosensor patch and/or wrist-worn biosensor data and smartphone data will be transferred via encrypted processes and will be stored in a secure server.

The clinical database will reside on a production server hosted by Medidata. All changes made to the clinical data will be captured in an electronic audit trail and available for review by Boston Scientific Corporation (BSC) or its representative. The associated RAVE software and database have been designed to meet regulatory compliance for deployment as part of a validated system compliant with laws and regulations applicable to the conduct of clinical studies pertaining to the use of electronic records and signatures. Database backups are performed regularly. Study data collected, reported, maintained and stored by the study vendor will be maintained by the study vendor on a secure server, with access allowed only by authorized individuals.

The Investigator provides his/her electronic signature on the appropriate electronic case report forms (eCRFs) in compliance with local regulations. A written signature on printouts of the eCRFs must also be provided if required by local regulation. Changes to data previously submitted to the sponsor require a new electronic signature by the Investigator acknowledging and approving the changes.

Visual and/or electronic data review will be performed to identify possible data discrepancies. Manual and/or automatic queries will be created in the EDC system and will be issued to the site for appropriate response. Site staff will be responsible for resolving all queries in the database.

13.1.1. Electronic Questionnaires

Questionnaires in electronic form may be collected directly on an electronic data collection platform at the clinical site (e.g. iPad). After completion by the subject/clinician, data from the electronic questionnaires will be transmitted directly into the EDC system.

[REDACTED]

[REDACTED]

[REDACTED]

13.2. Study Assessments

13.2.1. Chest-worn Biosensor Patch

The chest-worn biosensor patch (VitalConnect Sensor) is a commercially available battery-operated adhesive patch with integrated sensors and a wireless transceiver. It is worn on the torso and measures and records physiological variables that can include electrocardiography (ECG), skin temperature, activity and posture (body position relative to gravity). Data are transmitted wirelessly from the VitalConnect Sensor for storage and analysis.

Chest-worn biosensor patch wear requirements reflect total days. Subjects are encouraged to wear the patch for consecutive days however one day breaks are allowed in between patch changes. Breaks do not count towards the total.

13.2.2. Wrist-worn Biosensor

Subjects will also be asked to wear a commercially available wrist-worn biosensor, similar to a watch or wrist-worn fitness band. The wrist-worn biosensor will also collect biosensor data, such as heart rate and may be used to collect the pain log and respond to questions and/or questionnaires. Responses may be provided via voice responses.

The information collected from both the biosensors will be streamed to a secured data server. The wrist-worn biosensor may have other functionality removed.

13.2.3. Pain Log:

The NAVITAS study will utilize an off-the shelf, commercially available, customized smartphone or wrist-worn biosensor with the study-specific Pain Log loaded onto the device, as a data collection device. The subject will use the Pain Log to record changes in pain-level. The information collected will be streamed to a secured data server. The study-specific smartphone may have other functionality removed.

13.2.4. eDiary Application with Voice recording

The NAVITAS study will utilize an off-the shelf, commercially available, customized smartphone with the study-specific eDiary Application loaded onto the smartphone, as a data collection device. The subject will use the eDiary Application to respond to questions and/or questionnaires. Subject will also use voice recording in the eDiary Application to provide a brief (approximately two to five minutes) voice recording. Subjects will not be asked to record protected health information. Cell signal capability will be used to retrieve and report data to a secure data server. The study-specific smartphone will have other functionality restricted.

13.2.5. Fear Avoidance Beliefs Questionnaire (FABQ)

The Fear Avoidance Beliefs Questionnaire (FABQ) was developed by Waddell to investigate fear-avoidance beliefs among low back pain subjects in the clinical setting [20]. This survey is designed to assist in predicting which subjects may have a high pain avoidance behavior. This questionnaire consists of 16 items, with each item scored from 0-6. Higher scores on the FABQ are indicative of greater fear and avoidance beliefs.

The FABQ consists of 2 subscales. The first subscale (items 1-5) is the Physical Activity subscale (FABQPA), and the second subscale (items 6-16) is the Work subscale (FABQW). It is expected to take about three to five (3-5) minutes to complete.

13.2.6. Pain Catastrophizing Scale (PCS)

The Pain Catastrophizing Scale measures cognitive responses to chronic pain, specifically a subject's rumination, magnification and feelings of helplessness relative to their pain. It consists of thirteen (13) questions and is expected to take about three to five (3-5) minutes to complete.

13.2.7. Optional Magnetic Resonance Imaging

A thoracolumbar MRI may optionally be performed for the De Novo cohort to confirm spine anatomy and planned neurostimulator lead position. MRI of subject's spine and planned electrode location will be collected during Baseline period prior to Trial Procedure for the de novo cohort. If an MRI was performed up to 6 months prior to consent as per standard of care, it does not need to be repeated for study purposes.

13.2.8. Optional Computerized Axial Tomography (CT)

A CT scan of subject's spine and lead electrode location may optionally be collected after receiving the permanent neurostimulator implantable pulse generator implant, to confirm subject spine anatomy and placement of permanent neurostimulator Implantable Pulse Generator (IPG) lead position.

13.2.9. Fluoroscopy

Standard of care thoracic and lumbar imaging will be collected at the Neurostimulator Trial Stimulation Procedure and permanent neurostimulator IPG Implantation. Images should reflect

final lead spinal placement from these procedures and be marked to denote vertebral level. An optional thoracic and lumbar image may be taken to show the location of the leads in the spine at the End of Trial Procedure Visit for subjects who sign optional NAVITAS informed consent addendum

[REDACTED]

[REDACTED]

[REDACTED]

[REDACTED]

13.2.11. Adverse Events

Adverse event evaluation will be conducted to identify adverse events occurring during the study and classify them in regards to seriousness, relationship to the study procedure and/or device, action taken and outcome. All device-related and procedure-related adverse events, all serious adverse events and serious adverse device effects will be reported from the time of enrollment until the end of study participation.

13.2.12. Beck Depression Inventory (BDI-II)

BDI-II measures the intensity, severity, and depth of depression. It includes a long form of 21 questions, each evaluating a specific depression symptom (e.g., sadness, pessimism, irritability, loss of energy, concentration difficulty, indecisiveness, changes in sleep pattern, fatigue, etc).

13.2.13. Clinical Global Impression of Change (CGI-C)

CGI-C is a seven-point scale that requires the clinician to assess how much the subject's condition has improved or worsened relative to the subject's enrollment in the study. The clinician will rate the subject's change as: very much improved; much improved; minimally improved; no change; minimally worse; much worse; or very much worse.

13.2.14. Concomitant Medications

All prescribed pain-related medications will be collected throughout the study in order to obtain a full record of medication-related resource utilization. Information will include medication name, start and stop dates, indication or purpose, dose, frequency, and route of administration.

13.2.15. Demography

Demographic information will include birth year, birth day and month (if allowed by local regulations), gender, and race/ethnicity.

13.2.16. Ease-of-Use Questionnaire

The Ease-of-Use Questionnaire asks questions about the subject's ease in using the various device components. The questionnaire asks the subject to rate how strongly they agree or disagree with statements on how easy it is to use their stimulation device system. This questionnaire utilizes a 7-point scale ranging from 'completely agree' to 'completely disagree'. The ease-of-use questionnaire is a direct global measure of the patient's experience with the device.

13.2.17. End of Trial Period Evaluation

The End of Trial Period Evaluation is the clinician's professional assessment of whether the subject is a candidate for permanent implantation of a neurostimulation system based on the outcome of the subject's device trial.

13.2.18. End of Study

End of Study form will collect the date the subject completed participation in the study and the reason (i.e. completed study, withdrawal, etc.).

13.2.19. EQ-5D 5 Level (EQ-5D-5L)

EQ-5D-5L is a standardized measure of health status developed by the EuroQol Group in order to provide a simple, generic measure of health for clinical and economic appraisal. Applicable to a wide range of health conditions and treatments, it provides a simple descriptive profile and a single index value for health status that can be used in the clinical and economic evaluation of health care as well as in population health surveys.

EQ-5D-5L is comprised of a descriptive system and a visual analog scale. The descriptive system measures quality of life along five dimensions, including mobility, self-care, usual activities, pain/discomfort, and anxiety/depression, with five levels for each dimension from which subjects are asked to select one. The "thermometer" is a visual analog scale used to record the subject's self-rated health on a scale from 0 'the worst health you can imagine' to 100 'the best health you can imagine'.

13.2.20. Maintenance of Pain Coverage (MPC)

MPC consists of two items assessing new areas of pain that the subject has developed since first receiving neurostimulation treatment, as assessed by the treating clinician. Item one assesses whether the subject has developed any new areas of pain, and the second item assesses the extent of coverage by paresthesia in these areas.

13.2.21. Medical History

Medical history will include medical and procedural history relating to pain management, onset of chronic pain, and all pain-related diagnoses.

13.2.22. Oswestry Disability Index version 2.1a (ODI v2.1a)

Oswestry Disability Index questionnaire is to be used when the targeted pain area involves the back or legs.

ODI v2.1a assesses the degree of patient disability due to pain, measuring the impact of pain on activities of daily living. ODI v2.1a is composed of 10 questions that describe the pain and its impact on daily life on a 0-5 scale, with higher values indicating the more severe impact.

13.2.23. Pain Intensity

Pain Intensity is a questionnaire assessing the intensity of the subject's different areas of pain. Pain intensity is expressed on a 0 – 10 numerical rating scale (NRS), where 0 indicates “no pain” and 10 indicates “pain as bad as you can imagine”.

13.2.24. Paresthesia Coverage

Paresthesia Coverage assesses how much of the subject's painful areas are covered by neurostimulation-induced paresthesia. Paresthesia coverage is expressed as a percentage from 0 – 100%.

13.2.25. Patient Global Impression of Change (PGI-C)

PGI-C is a seven-point scale that requires the subject to assess how much their condition has improved or worsened relative to their enrollment in the study. Subjects will rate themselves as: very much improved; much improved; minimally improved; no change; minimally worse; much worse; or very much worse.

13.2.26. Percent Pain Relief (PPR)

PPR is a three-item questionnaire assessing how much of the subject's different areas of pain from before the pre-study neurostimulation trial has been relieved by the current neurostimulation treatment. Pain relief is expressed as a percentage from 0 – 100%.

Targeted pain is defined as areas of pain, indicated at Baseline that the clinician will attempt to address with the neurostimulation system.

13.2.27. Physical Exam

A complete physical exam will be performed by the clinician.

13.2.28. Procedure Information

General information will be collected regarding all neurostimulation procedures performed during the study, including all neurostimulation trial procedures and IPG implantation procedures.

13.2.29. Resource Utilization Inventory (RUI)

Health-related resource utilization data will be collected to support the health economic analyses. Resource utilization categories include: office/hospital visits, diagnostic tests, and non-surgical procedures

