20.2. Definitions and Classification

Adverse event definitions are provided in Table 20.2-1. Administrative edits were made on the safety definitions from ISO 14155 and MEDDEV 2.7/3 for clarification purposes.

Table 20.2-1: Safety Definitions

Term	Definition
Adverse Event (AE) Ref: ISO 14155 Ref: MEDDEV 2.7/3	Any untoward medical occurrence, unintended disease or injury, or any untoward clinical signs (including an abnormal laboratory finding) in subjects, users or other persons, whether or not related to the study medical device. NOTE 1: This includes events related to the study medical device or comparator. NOTE 2: This definition includes events related to the procedures involved. NOTE 3: For users or other persons, this definition is restricted to events related to the study medical device.
Adverse Device Effect (ADE) Ref: ISO 14155 Ref: MEDDEV 2.7/3	Adverse event related to the use of the study medical device NOTE 1: This includes any adverse event resulting from insufficiencies or inadequacies in the instructions for use, the deployment, the implantation, the installation, the operation, or any malfunction of the study medical device. NOTE 2: This definition includes any event resulting from use error or intentional abnormal use of the study medical device.
Serious Adverse Event (SAE) Ref: ISO 14155 Ref: MEDDEV 2.7/3	Note: This definition meets the reporting objectives and requirements of ISO 14155 and MEDDEV 2.7/3. Adverse event that: a) Led to death, b) Led to serious deterioration in the health of the subject as defined by either: 1) a life-threatening illness or injury, or 2) a permanent impairment of a body structure or a body function, or 3) in-patient hospitalization or prolongation of existing hospitalization, or 4) medical or surgical intervention to prevent life-threatening illness or injury or permanent impairment to a body structure or a body function c) Led to fetal distress, fetal death, or a congenital abnormality or birth defect.

Table 20.2-1: Safety Definitions

Term	Definition
	NOTE 1: Planned hospitalization for a pre-existing condition, or a procedure required by the clinical investigational plan, without a serious deterioration in health, is not considered a serious adverse event.
Serious Adverse Device Effect (SADE) Ref: ISO 14155 Ref: MEDDEV 2.7/3	Adverse device effect that has resulted in any of the consequences characteristic of a serious adverse event.

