1. For the purposes of this study, hospitalization is defined as any in-patient admission.
2. Hospitalizations occurring for the purpose of performing a planned procedure as per routine care such as implant procedures, or follow-up visits, are not to be reported as a SAE. However, complications or adverse events that occur during the planned procedure should be reported as (S)AEs if they meet the protocol specified definitions.
3. Elective/planned hospitalization(s) need not be reported as an SAE. However, complications or adverse events that occur during an elective/planned hospitalization, should be reported as (S)AEs if they meet the protocol specified definitions.
4. In the event of subject death during the conduct of the study, efforts should be made to perform an autopsy.
5. Sensations or side effects that occur during the programming session should not be reported as AEs. However, sensations or side effects caused by the final programming parameters (including active contact, pulse width, frequency, and amplitude) that persist or occur after the completion of the programming will be reported as AEs.
6. Lack of efficacy/decreased therapeutic response will not be collected as AEs. Also, return of the patient's pain symptoms to their pre-SCS level does not meet the criteria for an AE.
7. Clinically significant worsening of symptoms, beyond the pre-SCS symptoms or the expected course or progression of the disease, should be reported as an AE.
8. Device/lead migration will not be collected as an AE. However, if the device/lead migration precipitated an AE, the AE should be reported in the *Adverse Event* eCRF. Device/lead migration should be documented in the *Device Deficiency* eCRF.
9. Device deficiencies, failures, malfunctions, and product nonconformities should not be reported as adverse events. However, if an adverse event resulted from a device failure or malfunction, that specific event would be recorded on the *Adverse Event* eCRF. Device deficiencies, failures, malfunctions, and product non-conformities should be documented in the *Device Deficiency* eCRF.

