12.4.19. Procedure Information

General information will be collected regarding the SCS procedures performed during the study, including all neurostimulation trial procedures and IPG implantation procedures.

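### No readable field in NAVITAS or ENVISION identifies a non-neurostimulation operation during follow-up, so its effect cannot be separated from that of stimulation

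*Combined protocol and SAP*

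**What the plan says.** NAVITAS 13.2.29 gives the inventory's purpose: "Health-related resource utilization data will be collected to support the health economic analyses". It then lists the content: "Resource utilization categories include: office/hospital visits, diagnostic tests, and non-surgical procedures". The neighbouring form, 13.2.28, says "General information will be collected regarding all neurostimulation procedures performed during the study, including all neurostimulation trial procedures and IPG implantation procedures". ENVISION 12.4.19 is equivalent: "General information will be collected regarding the SCS procedures performed during the study, including all neurostimulation trial procedures and IPG implantation procedures". ENVISION's readable assessments include no resource inventory.

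On safety reporting, Note 3 in NAVITAS 20.2 reads "Elective/planned hospitalization(s) need not be reported as an SAE", and Note 3 in ENVISION 17.2 carries the same rule. Table 20.2-1 in NAVITAS likewise keeps a planned admission for a pre-existing condition outside the SAE definition, unless health seriously deteriorates. In both plans, non-serious events are collected only when related to the device or procedure (NAVITAS 20.4, ENVISION 17.4).

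For medication, NAVITAS 13.2.14 collects all prescribed pain drugs with dates and indication. ENVISION 12.4.3 collects opioids only.

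**The concern.** Section 4.1 of each plan names intraspinal injections, pulsed radiofrequency and back surgery among the treatments for this pain. A subject can receive one of them during follow-up, which runs to 36 months in NAVITAS and to about 48 months for the ENVISION Extension Cohort (synopses). Such a treatment may change pain, walking and sensor-measured activity together. If its date and type are not in the database, the analyst can neither flag it nor censor at it, and later analysis cannot recover them.

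Three uses of the data are exposed:

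- Both plans model treatment parameters against clinical outcomes (NAVITAS 12.1.1.3, ENVISION 11.1.1.3). Medication use is a named subgroup factor; other procedures are not.
- ENVISION may turn observed relationships into recommendations and evaluate their effect (section 6).
- The NAVITAS inventory feeds a health economic analysis, and non-neurostimulation surgery may be a large cost item.

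**Working it through.** The documents state no figure that depends on this point, so there is nothing to reproduce. The check traces each readable route by which a non-neurostimulation procedure could enter the database.

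| Route | NAVITAS | ENVISION |
|---|---|---|
| Procedure form | Neurostimulation only (13.2.28) | SCS only (12.4.19) |
| Resource inventory | Visits, tests, non-surgical procedures (13.2.29) | None described |
| SAE, planned admission | Exempt (20.2) | Exempt (17.2) |
| SAE, unplanned inpatient operation, or complication of a planned one | Reportable if it meets the definition | Reportable if it meets the definition |
| Medication | All prescribed pain drugs, dated, with indication (13.2.14) | Opioids only (12.4.3) |
| Medical history | Pain-related procedural history; not described as an on-study log (13.2.21) | Same (12.4.12) |
| Site charts | Retained at site (11.24) | Procedures listed, but retained at site (10.11) |

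**NAVITAS.** An injection or radiofrequency procedure fits the inventory. A planned operation does not fit as an operation. It may show as a hospital visit and as new pain medication, but neither entry says that surgery took place.

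**ENVISION.** An outpatient injection or radiofrequency procedure involves no admission, so the hospitalisation criterion does not bring it in. With no inventory, an opioid entry is the only visible trace of it or of a planned operation.

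**Analysis.** The readable statistical text (NAVITAS 12.1.1.3 and 12.3; ENVISION 11.1.1.3 and 11.3) has no rule to flag, adjust for or censor at such a procedure.

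**Size, on assumed inputs only.** Let f be the share of subjects with an unidentified procedure and d its effect on the 0–10 NRS. If all effects act in the same direction:

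shift in cohort mean = f × d

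- Low: f = 2%, d = 1 gives 0.02 × 1 = 0.02 points.
- High: f = 10%, d = 3 gives 0.10 × 3 = 0.30 points.

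Neither f nor d comes from the documents. Effects in mixed directions would give a smaller shift. A subgroup in which procedures cluster, for instance one defined by pain diagnosis, would have a larger f and a larger shift. Within an affected subject, only d is due to the procedure; the rest of the change is not.

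**The case against.** The strongest reply is that much may be hidden by redaction or not shown. This applies to the data collection tables, several eligibility criteria in both plans, NAVITAS 13.2.10, parts of the NAVITAS 12.1.1.3 and 12.2 text, and ENVISION 11.2, 12.3 and 12.5. A procedure log, a planned-surgery exclusion or a covariate rule could sit there. The readable exclusions EC2 (NAVITAS) and EC4 (ENVISION) already let the investigator exclude conditions or external factors that might confound outcomes, and the questions in the ENVISION mobile app are not itemised. This limits confidence, but does not remove the point. The sections that define procedure and resource capture are unredacted, and ENVISION's assessment list runs unbroken from 12.4.1 to 12.4.22. An entry criterion also cannot record a procedure that arises later.

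Two stronger readings are tempting and are not supported:

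- *A reader might infer that a planned operation leaves no record.* In NAVITAS it may leave the indirect traces above, and the inventory's list may not be meant as exhaustive. In ENVISION, Table 17.2-1 excludes elective surgery from hospitalisation only if it was pre-planned and documented at consent or enrolment, which is narrower than Note 3.
- *A reader might infer that the operation's effect is credited to stimulation.* The plans have no hypotheses or pre-defined endpoints, and they model correlations. An operation biases a parameter–outcome estimate only if it is associated with the parameters; otherwise it adds noise. If it moves pain and activity together, the metric–outcome association is real covariation. What can be said is that the two sources of change cannot be told apart.

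**Conclusion.** The point holds as a gap in data capture. No readable field in either plan identifies a non-neurostimulation operation during follow-up. In NAVITAS the identity as surgery is missing, though indirect traces may exist. In ENVISION the gap is wider and also takes in non-SCS injections and radiofrequency procedures. Their effect on outcomes and sensor data cannot be separated from that of stimulation, and the NAVITAS cost analysis would omit non-neurostimulation surgery.

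The size cannot be derived from the documents. The illustrative shift in the cohort mean is 0.02 to 0.30 NRS points, which is small at the lower end. The conclusion rests on the readable text and would fall if a redacted table contained the field. Because the work is exploratory and the average effect is probably modest, this is a cheap improvement rather than a flaw that undermines the study. It has to be made while data are being collected.

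**What to change.** 1. In NAVITAS 13.2.29, replace the non-surgical category with: *surgical and non-surgical procedures for pain or the musculoskeletal system, with date and type*.
2. Add the same dated log line at ENVISION visits.
3. Include surgery in the NAVITAS cost total.
4. In both plans, add one sensitivity analysis that flags outcome and sensor data from the first such procedure onward, or censors them at that date.

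If a redacted table already holds such a field, a cross-reference to it and step 4 are enough, provided that surgery enters the cost total. The cost is one extra eCRF line per visit and one extra analysis. Clinical management is unchanged.
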